#### A4b. Aim 2.

Study/Design overview: This aim is phase 1 focusing on the formative development of the eHealth intervention using a human-centered design (see Appendix 2). *Guiding the development of this Aim (and Aim 3) will be Levesque’s Framework which proposes that patient’s ability to engage is at the core of successful health care consequences (i.e., outcomes). Therefore, the focus will be on providing patients the mechanism to initiate treatment. This will be done via active self-monitoring and specific labeling of depression symptoms, as well as via emotional and practical support. Based on this framework, the process by which behavior change about treatment is activated is by helping patients more clearly identify health care needs (i.e., via symptom monitoring) help rectify perception of needs (by providing feedback on symptoms, whether they are elevated and a provider should be contacted), helping with care seeking and reaching (i.e., sending provider contact information and sending reminders).*

Sample: This aim will be achieved by involving 10 stakeholders (patient n = 6 and provider n = 4). Patients will be selected based on risk scores generated in Aim 1 and the following inclusion/exclusion criteria. Patient and provider input will be used to revise intervention content.

Table 2. Patient inclusion/exclusion criteria for Aims 2 and 3.

Inclusion criteria:

- OEF/OIF Veteran: high prevalence of depression in this population and generalizability across adult ages
- PHQ9 $\geq 10$ ; DSM-5 criteria for major depressive disorder will be used to extract an MDD diagnosis.
- No gender or minorities will be excluded from this study; all ages will be included.

Exclusion criteria:

- Current/Past Bipolar disorder and Current Psychotic disorder: to avoid potential exacerbation from treatment for depression
- Alcohol Use disorder or Substance Use disorder: Depression treatments cannot reverse the adverse effects of substances on mood, and therefore impact on adherence and treatment characteristics may be confounded

- Other current severe or unstable, psychiatric and medical disorders that necessitates clinical management that can confound results (e.g., cancer [in chemotherapy], suicidality, recent hospitalization [medical/surgical] for which recovery overlaps with study onset and duration, open skull/brain injury, moderate to severe TBI)
- Moderate to severe cognitive impairment (SLUMS  $\leq 20$  and/or diagnosis in medical record)
- Potentially temporary states/situations that may significantly impair mood/capability to engage in treatment: unstable environment that is not in one's control (e.g., homeless, temporary group home, extensive care taking duties).

Sampling plan: The target population is a clinical sample of Veterans with depression who meet the criteria in Table 2. Exclusion criteria are consistent with conventional depression studies. Veterans will be excluded if they have a medical disorder that would significantly increase their risk of depression secondary to a medical diagnosis or due to treatments for those medical diagnoses (e.g., cardiovascular disease; SUD) or those experiencing side effects with standard treatment or would require a significant adaptation of treatment (e.g., bipolar disorder). Veterans will also be excluded consistent with the standard of care for cognitive and/or behavioral treatment of depression at Tampa VA (e.g., actively suicidal patients that need intensive and immediate treatment). Patients will need to have a risk score associated with lack of treatment initiation as determined in Aim 1.

Recruitment: The Tampa VA is an ideal site because it has a large and diverse mental health population. In FY17 over 2000 patients had a first visit to primary and specialty mental health care, with over half showing a depression diagnosis in their charts. Veterans will be recruited using the following methods: 1) Depression treatment consults. Veterans referred for mental health treatment (psychotherapy or medication) through the mental health consult service will be informed about the proposed CDA clinical trial either by their provider or the study RA who will regularly monitor MH referrals on CPRS. 2) Advertisement. IRB-approved brochures will be placed throughout Tampa VA (e.g., primary care, pharmacy). Interested Veterans can contact study staff to learn more about participating. 3) Referrals from providers. Tampa VA providers in primary care - mental health service lines will be informed of the study and given research brochures. Providers can then give information to Veterans referred to specialty care for treatment.

Ability to recruit, retain, and justification for sample: A sample size of 10 stakeholders (both patients and clinicians) is in line with samples utilized in human centered designs, given the richness of the data being collected. Patient sample size is clearly attainable given the Primary Care clinic volume at the Tampa VA. I have access to patients given my direct patient contact through my clinical appointment with the Primary Care clinic. The Tampa VA PCMHI/PACT clinics have 12 psychologists and 1 psychiatrist, most of whom I have had direct contact with and therefore interviewing 4 clinicians would be highly feasible. Both [name] (Supervisory Psychologist for the Primary Care clinics) and [name] (Psychology Section Associate Chief) have approved and are supportive of my data collection in the primary care and mental health clinics at the Tampa VA (see letters of support). I have ample experience with recruitment and retention of participants with mental illness. My involvement in the Women's Center PCMHI clinic will ensure women are represented.

#### Procedures and Methods:

*Intervention content.* I am currently in the process of building an initial draft of the intervention in Qualtrics to prepare for formative development. The intervention has three features (see Appendix 2): depression symptom and mood monitoring designed to increase engagement (i.e., treatment initiation), practical support (i.e., appointment reminders), and emotional support (i.e., encouraging messages). Symptom monitoring will be accomplished through repeated assessment of depression symptoms with the PHQ9 (with the exception of the suicide item which will be excluded in concordance with IRB approved protocols in the past). Mood will be monitored using a mood adjective list composed of 7 positive mood adjectives (talkative, enthusiastic, confident, cheerful, energetic, satisfied, and happy) and 7 negative mood adjectives (tense, anxious, distracted, restless, irritated, depressed, guilty). Specifically, participants will be asked to report on the PHQ9 (except the suicide item): 1. The 8 depressive symptoms by rating each one in turn from 0 to 3 (0 "none of the time", 1 "less than half the time", 2 "more than half the time", 3 "most or all of the time", in the past 24 hours). They will also be asked to rate the 14 different adjectives on an analog scale of 0-100. Finally, they will be asked whether anything has happened since the last report to trigger a symptom change (both positive and negative events). Patients will be asked to report how important, expected, pleasant, unpleasant, and stressful this event was on an analog scale of 0-100. Assessments will be completed through online surveys. Practical support will consist of reminders of upcoming mental health appointments. Emotional support will be encouraging messages thanking patients for reaching out and prioritizing their mental health needs. A list of possible messages will be created as a result of our interviews with our patient and provider stakeholders. Practical and emotional support messages will be delivered through push texts (i.e., texts that don't require a response).

*Intervention programming.* The intervention will use a daily diary assessment procedure and is programmed using an electronic platform, i.e. Qualtrics. Qualtrics is approved by VA central office for research use. Qualtrics

has an ATO agreement for use for government data collection as it is the only Experience Management Platform with FedRAMP authorization, ISO 27001 certification, and FISMA compliance. The intervention will be on a set schedule to deploy once a day in the evening when patients would receive a text prompt to respond to questions described in the prior section which is estimated to take 5-10 minutes, or patients may receive a push text message with information only (practical or emotional support). Qualtrics has the capacity to automatically deploy contact information for the patient's provider when respondents' depression score is elevated beyond a clinical cut-off point of 15 (indicative of moderately severe depression which likely warrants treatment for depression using antidepressant, psychotherapy, or a combination of treatments).

**Phone screening.** Veterans interested in participating will initially contact the study research assistant (RA) by phone and participate in a phone screen for eligibility. Alternatively, an RA will be checking for new mental health referrals to the mental health clinic and contact patients, initially via mail and later by phone per VA approved procedures. The screening interview was developed and used at USF for screening participants for NIH funded grants and the PI's dissertation. The interview will assess for inclusion and exclusion criteria in Table 2. Veterans who are eligible following the phone screen will be invited to a face-to-face session. Veterans will be informed that study participation does not affect their usual mental health care. Patients that present with mental health emergencies will be screened with the CSSRS per VA policies and VA police will be contacted if patient is deemed to need emergency care.

**Data collection.** Informed consent. The initial face-to-face session will include answering questions, addressing concerns, and administering written informed consent. After written informed consent, participants will be enrolled in the study and qualitative interviews will be performed when a draft of the intervention is tested.

**Stakeholder qualitative interviews.** Semi-structured interviews will be conducted as part of my training in human centered design methodology with guidance from [name], co-primary mentor on this application. The interviews will be completed in-person. The interviews will be conducted using a semi-structured interview guide (see Appendix 3) and rapid iterative process which would allow for more in-depth questioning where appropriate. All interviews will be audio recorded with participant permission and written notes will be used to support rapid iterative analysis. Interviews will be transcribed verbatim for final analysis. The initial interview guide will address needs, benefits, expected challenges, and suggested modifications associated with the proposed intervention as stakeholders are given an opportunity to use it and experience it in vivo while they trial a preliminary version of the intervention. Follow-up prompts will be used as needed to obtain rich descriptions of interviewee experiences and needs. Feedback will be sought about the functionality of the intervention, its perceived use, and ways to enhance it, including suggestions for emotionally supportive messages patients may want to see as they prepare to attend mental health sessions. The intervention will be subsequently revised with the feedback received during this process in preparation for active data collection for Aim 3.

**Qualitative Data Collection and Analysis.** Data collection and analysis will occur concurrently allowing for insights from data analysis to iteratively guide subsequent data collection (e.g., modification of interview questions). This data will be analyzed using an NCT analysis model (Seidel, 1998). The NCT model was chosen because it was specifically developed for computer-assisted qualitative data analysis software (CAQDAS). This approach consists of three basic components: noticing, collecting, and thinking about interesting things in the data. The NCT model uses coding structures, memoing, process mapping, and diagramming to describe, categorize, and connect the data. This process helps to determine common themes, patterns, and inconsistencies relating to the interviewees' experiences, perceptions, and opinions. Interview transcripts will be uploaded into ATLAS.ti v8.0. This CAQDAS will assist me in the systematic development of a code book which consists of operationalized codes and thematic categories. Memoing and analytic writing will be done at each step of the analysis to document the process and to develop conceptual ideas relevant to the data. I will meet routinely with [name] to review ongoing coding results, resolve coding issues that arise, and discuss the development of thematic coding categories. Interrater reliability with a second coder will be used in the development of the code book and to ensure internal validity of the analytic process.

**Data Security.** Raw interview data including field notes and audio files will be stored in a locked filing cabinet in the PI's office. Interviews will be transcribed verbatim and saved on a secure server behind the VA firewall.

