#### **A4. RESEARCH DESIGN AND METHODS**

*Aim 1 consists of an analysis of data extracted from the EHR to identify risk profiles (scores) and determine which patients are unlikely to engage in care for depression. These risk scores will be used to select patients for a proposed intervention that will be developed in Aim 2 and subjected to a formative evaluation in Aim 3. The intervention is technology-based and includes automated symptom assessment with emotional and practical support texts to provide interim support to Veterans referred to mental health care who are awaiting their initial mental health treatment visit.*

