**Data processing.** Data will be initially checked for out of range values and missing data where appropriate through plotting and descriptive analyses. Data will be transformed as needed. Logistic regression is relatively free of restrictions and can accommodate a mix of predictors (continuous, discrete, dichotomous) (Tabachnick & Fidell, 2007). *With continuous predictors, the assumption is that there is a monotonic relationship (increase or decrease) between the predictor variable and odds of the binary outcome (i.e. engagement or lack of engagement in care). The functional of this linear assumption can be evaluated by use categorical indicator variables as well as transformations of the continuous variable, such as a quadratic form. Multicollinearity will be tested using two approaches. First, we will explore correlations among IVs and exclude variables based on high correlations ( $> .65$ ). Second, we will examine the size of the standard error (SEs) relative to the beta coefficient for each predictor in the model. Large SEs will be indicative of potential multicollinearity. Residuals will be tested to identify possible outliers.*

Analysis plan:

**Modeling risk for lack of treatment engagement.** For all analyses, lack of treatment engagement is the main dependent variable and will be investigated using three related definitions based on the date in which a PHQ9 score  $\geq 10$  is identified in the EHR. Specifically, we will examine whether treatment is initiated within 3-months, 6-months, or 12-months from the date of the PHQ9 assessment. *Independent variables of interest will be extracted based on proposed framework, empirical evidence, and availability in the EHR (see Table 1), including insight from a select number of semi structured surveys collected prior to data analysis (described below).*

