#### **A4c. Aim 3.**

**Study/Design Overview:** Aim 3 will focus on completing phase 2 of the eHealth intervention development, which will be a formative evaluation. For this portion of the study we will collect both qualitative and quantitative data from a new sample of patients using same inclusion/exclusion criteria in Table 2. This portion of the study will help to determine usability, acceptability, engagement with the intervention, and potential problems with completing the intervention and collecting data in a complete and rigorous manner.

Participant recruitment and sampling: Participant recruitment and sampling will follow steps described in Aim 2. The sample size selected for this aim (n=15) is in line with samples recommended for formative evaluations and pilots. The sample is attainable based on rationale presented in Aim 2. The analytical rationale for the sample size is based on the proposed analyses presented below.

Procedures: Veterans recruited for this aim will be asked to complete 1) baseline questionnaires to understand the clinical make-up of the sample and unobserved patient characteristics that may impact our formative evaluation findings, 2) the intervention, and 3) a semi structured interview to complete the formative evaluation.

Self-report measures: These quantitative measures will be used to better understand the makeup of our sample in terms of clinical characteristics and treatment readiness that may not otherwise be observable from the structured data in their EHRs: **Patient Health Questionnaire 9 (PHQ-9)**, 9-item instrument that assesses the symptoms of depression corresponding to the Diagnostic and Statistical Manual Version 5 (DSM-5) diagnostic criteria for a major depressive episode. Item responses are on a four-point scale (from occurring “not at all” to “nearly every day” over the past two weeks) resulting in a score range from 0 to 27. The PHQ-9 has similar psychometric properties to other measures of depression. PHQ-9 is favored for its brevity and ease of use in clinical settings (Cameron et al, 2011).

**Posttraumatic Stress Disorder Check List for DSM-5 (PCL-5)**, 20-item self-report of the severity of PTSD symptoms in the past month using a 5-point scale (0-4), ranging from “Not at all” to “Extremely.” A cut-point of 50 (range 0-80) represents a probable diagnosis of PTSD.

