*Data Analysis. First, descriptive analyses will be performed on all baseline patient characteristics extracted for all patients approached for study enrollment, including those who agreed and did not agree to participate. To compare these two groups, we will use student t-tests (for continuous variables) and chi-square analysis (for categorical variables). This information will be used to derive acceptability of the proposed intervention. Next, descriptive analyses will be performed on the baseline questionnaires collected from the group of participants enrolled. This will give us additional data about patient characteristics that may further refine our phenotypes or improve study feasibility in the future. Engagement will be derived from percentage of prompts completed per days of participation in the intervention. Finally, we will calculate rates of treatment initiation (and corresponding 95% confidence interval) and compare to the initiation rate identified in our recent study on the Aim 1 cohort. To compare study treatment initiation to rates observed in Aim 3 to those in Aim 1 sample we will calculate the 95% confidence interval (CI) for the difference score between proportions (see Franklin, 2007). A significant difference will be denoted if the 95% CI does not include zero (Cumming & Finch, 2005). I will use negative binomial regression which accounts for overdispersion if treatment initiation is low (Coxe, West, & Aiken, 2009).*

Qualitative interviews and analysis: The interviews will be conducted using a semi-structured interview guide (see Appendix 3) and the same methods as Aim 2 interviews and analysis. These interviews will focus on the user's experiences using the self-monitoring intervention. Feedback will be sought about the functionality of the intervention, its perceived use, and ways to enhance it. We will specifically inquire about patients' perceptions about the three parts of the intervention: the symptom self-monitoring, practical support (i.e., appointment reminders), and emotional support (i.e., encouragement). Patients will also be asked to provide suggestions for emotionally supportive messages patients may want to see as they prepare to attend mental health sessions. Qualitative data will be analyzed in the same manner as presented in Aim 2.

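### The Aim 3 initiation rate is compared with an Aim 1 rate that starts its clock earlier, at the PHQ9 date, with no allowance for delayed entry

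*Protocol*

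**What the plan says.** **Aim 1 clock.** Protocol A4a takes Veterans who were not in depression treatment before the index PHQ9, and "we will examine whether treatment is initiated within 3-months, 6-months, or 12-months from the date of the PHQ9 assessment". Initiation means a specialty mental health or primary care encounter, other than an assessment, linked to a depressive diagnosis. Referral is not required for the Aim 1 cohort.

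**Aim 3 entry.** Protocol A4 describes the intervention as interim support for "Veterans referred to mental health care who are awaiting their initial mental health treatment visit". A4c states that "Participant recruitment and sampling will follow steps described in Aim 2". Under those steps a research assistant may find new referrals and then "contact patients, initially via mail and later by phone per VA approved procedures". Alternatively, a provider may refer, or a brochure may prompt contact ("Interested Veterans can contact study staff to learn more about participating"). After screening, "Veterans who are eligible following the phone screen will be invited to a face-to-face session", where written consent is taken.

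**Comparison.** A4c will calculate the Aim 3 initiation rate and "compare to the initiation rate identified in our recent study on the Aim 1 cohort", using a 95% confidence interval for the difference between proportions and calling it significant if zero is excluded. The SAP keeps this rule but takes the comparator from the literature, without naming a source or figure. Neither document says when the Aim 3 clock starts, how long it runs, or how treatment status at enrolment is recorded.

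**The concern.** The two proportions have different time origins. The Aim 1 rate includes Veterans who start care in the first days or weeks after the PHQ9. A Veteran who starts that quickly is no longer waiting for a first visit when Aim 3 consent is taken. This is delayed entry (left truncation). Matching the groups on risk score, referral or window length would not remove it.

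If the Aim 3 clock runs from the PHQ9, participants untreated at enrolment have, by construction, no event in the time before enrolment. If it restarts at enrolment, the participants are those who did not start early, and they may be slower starters in general. This is the plan's only comparison on treatment initiation, and Aim 3 is meant to prepare a follow-on RCT. A point estimate that mixes the intervention with entry time is a poor guide for that trial.

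**Working it through.** **No figure in the plan to reproduce.** The documents give no Aim 1 initiation rate, no delay from PHQ9 to enrolment and no Aim 3 window. The sample size of 15 is justified by convention, without power inputs. The size of the effect can therefore only be bracketed.

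**Inputs**
- Benchmark p = 27% or 18.5%. These are the ends of the range in Protocol A1 for any mental health care utilization, used as a stand-in.
- Window W = 90 or 365 days, the shortest and longest Aim 1 windows.
- Delay d = 14, 30 or 45 days from PHQ9 to enrolment (assumed).
- Weibull shape k = 0.6, 0.8 or 1.0 (assumed); 1.0 is a constant start rate and lower values are front-loaded.
- All Aim 3 participants are untreated at enrolment, and the intervention has no effect.

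**Formulas**
- Cumulative hazard: H(t) = -ln(1-p) × (t/W)^k
- Clock from PHQ9 to day W: 1 - exp{-(H(W) - H(d))}
- Clock restarted at enrolment for W days: 1 - exp{-(H(W+d) - H(d))}

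**One case in full** (p = 27%, W = 90, k = 0.6, d = 30): H(90) = 0.3147, H(30) = 0.1628, H(120) = 0.3740.
- Started before enrolment: 1 - exp(-0.1628) = 15.0%.
- Clock from PHQ9: 1 - exp(-0.1519) = 14.1%, which is 12.9 points below 27%.
- Clock restarted: 1 - exp(-0.2112) = 19.0%, which is 8.0 points below.

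**Range over the grid**

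| Benchmark | Window | No-effect rate, clock from PHQ9 | Shift (points) | No-effect rate, clock restarted | Shift (points) |
|---|---|---|---|---|---|
| 27% | 3 months | 10.2–23.3% | 3.7–16.8 | 17.6–27.0% | 0–9.4 |
| 27% | 12 months | 20.2–26.1% | 0.9–6.8 | 21.9–27.0% | 0–5.1 |
| 18.5% | 3 months | 6.7–15.9% | 2.6–11.8 | 11.8–18.5% | 0–6.7 |
| 18.5% | 12 months | 13.6–17.9% | 0.6–4.9 | 14.9–18.5% | 0–3.6 |

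The shift is largest at k = 0.6, d = 45. With a restarted clock it is exactly zero at k = 1.0.

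**Check without a Weibull curve.** Let f be the share of benchmark starters who start before enrolment. With the end date kept, the no-effect rate is q = p(1-f)/(1-fp). At p = 27%, q is 25.0%, 21.7% and 15.6% for f = 0.10, 0.25 and 0.50. At p = 18.5% it is 17.0%, 14.5% and 10.2%. The sign is the same and the sizes are similar.

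**What would cancel it.** Since q/(1-q) = (1-f) × p/(1-p), opposite selection with an odds ratio of 1/(1-f) offsets the shift: 1.11, 1.33 and 2.0 for those three values of f.

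**Precision at n = 15.** At 27% the standard error is √(0.27 × 0.73/15) = 11.5 points, so the 95% half-width is about 22 points. Treating the benchmark as fixed at 27%, the chance that a no-effect intervention gives an interval wholly below it is as follows:

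| Interval | f = 0 | f = 0.10 | f = 0.25 | f = 0.50 |
|---|---|---|---|---|
| Wilson | 0.9% | 1.3% | 2.5% | 7.8% |
| Wald | 5.8% | 8.1% | 13.1% | 29.6% |

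At a benchmark of 18.5% a Wilson interval can never lie wholly below it, because 0/15 already has an upper limit of 20.4%.

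**The case against.** A reader might infer that Aim 3 can enrol only Veterans who have not started care, that the bias must run against the intervention, and that an ineffective intervention would therefore look harmful. The documents do not support that reading.

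- **Eligibility.** Protocol Table 2 has no criterion on treatment already started. The restriction comes from design text describing Veterans "who are awaiting their initial mental health treatment visit". Waiting for a mental health visit is also not the same as being event-free: Aim 1 initiation counts primary care encounters with a depression diagnosis, so some participants may already be initiators under that definition.
- **Delay.** No delay is stated. Mail followed by phone is one route among several. Since phone screening checks the Table 2 criteria, which include a PHQ9 of at least 10, the qualifying PHQ9 might even be taken at screening, leaving a short gap.
- **Direction.** Aim 3 participants are referred, consent and attend in person; Aim 1 requires none of these. That plausibly raises initiation, and modest odds ratios would cancel the shift. Selection on a high risk score acts the other way.
- **Consequence.** Aim 3 is mainly about usability, acceptability and engagement, and 15 patients could not show a difference of several points in any case.

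These points stand, and they limit the claim on size and net direction. They do not remove the misaligned time origins: every route still passes through screening and in-person consent, and neither document aligns the clocks. A possible offset from unmeasured selection is no reason to leave in a component that can be removed cheaply. The SAP's literature comparator does not help, since its time origin is unknown and a published rate usually cannot be restricted to patients still untreated at a given time.

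**Conclusion.** The concern holds in limited form. The planned difference subtracts a rate counted from the PHQ9 date from one measured in people who enter later. To the extent that those people are untreated at enrolment, delayed entry taken alone lowers the Aim 3 rate relative to the benchmark. It leaves the rate unchanged only if the start rate is constant and the clock restarts at enrolment; only a start rate that rises over time would reverse the sign.

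The size depends on the assumed delays, hazard shapes and stand-in rates, and strongly on the unstated window. At 27%, the upper end falls from 16.8 points at 3 months to 6.8 at 12 months with the clock from PHQ9, and from 9.4 to 5.1 with a restarted clock. The net direction of the whole comparison cannot be determined from the documents. A conclusion that an ineffective intervention will appear harmful goes too far: with 15 patients and Wilson limits that result is uncommon unless a large share starts early, though Wald limits make it more frequent and the interval formula is not spelled out in the documents.

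**What to change.** Amend the Aim 3 data analysis text in the protocol and the matching SAP text as follows.

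1. For each Aim 3 Veteran, record the index PHQ9 date, the enrolment date, and whether treatment has already started under the Aim 1 definition, including primary care encounters. Define which PHQ9 is the index.
2. State the Aim 3 time zero and follow-up window.
3. Use a landmark benchmark. For a Veteran enrolled d days after the index PHQ9, take the Aim 1 Veterans still untreated at day d, and count initiation in both groups from day d over the same window with the same definition. Average these conditional Aim 1 rates over the enrolled Veterans. Report any participant who had already started treatment separately.
4. Use this benchmark in both documents, in place of the SAP's unspecified literature rate.
5. Present the difference with its interval as descriptive and drop the significance rule, because selection on referral and consent remains and n = 15 is imprecise.

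The cost is one further calculation on the existing Aim 1 extract and one added date per Veteran, with treatment status read from the record. No extra patients are needed. The reference rate will probably be lower than the unconditional Aim 1 rate.
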